## 2.4 Economic Evaluation Outcomes

Cost Outcomes	Brief Description of Measures	Measured By	Time Frame
Cost and incremental cost-effectiveness	
Health care utilization and intervention costs will be assessed.
 
Our primary measure of effectiveness (utility) at 12 months will be quality-adjusted life years (QALYs) gained
 
We will also estimate the incremental cost per additional patient with a MCID (30% from baseline) reduction in the RMDQ at 12 months.
	
Healthcare utilization costs: EHR data costed using standard costing algorithms [1 2] and Medicare fee schedules
 
Intervention costs: Acupuncture sessions will be tracked in study records and priced using typical community rates
 
Utilities will be estimated using the EQ-5D-5L and be used to calculate QALYs gained
 
PRO of scores from RMDQ at baseline and 12 months
	
Patient health care utilization costs from baseline to 12 months net of their utilization from the previous adj 12 months
 
EQ-5D-5L: Patient self-report at baseline, 3-, 6- and 12-months

### 3. Additional Variables for Effectiveness Analyses (Moderators and Predictors)

The following predictors/covariates and/or **moderators** will be assessed related to the **primary outcome**. Note: variables pre-specified for baseline adjustment in all models include: baseline outcome value, age, sex, race, and healthcare system

Moderators & Predictors	Definition	Role	Data Source
Sex	Male vs. Female/Other Sex at birth as reported by subject; assessed using HEAL CDE Demographic question	Moderator/Predictor	Patient self-report at baseline
Age	65-74, 75-84, 85+	Moderator/Predictor	EHR
Race/Ethnicity	White, non-white	Moderator/Predictor	Patient self-report at baseline
Expectations of acupuncture	EXPECT 1-item question – categorical based on the distribution of responses	Moderator/Predictor	Patient self-report at baseline
RMDQ	<18, 18+	Moderator/Predictor	Patient self-report at baseline
Pain catastrophizing	6-item subscale required by HEAL CDE	Predictor/covariate	Patient self-report at baseline

Moderators & Predictors	Definition	Role	Data Source
Fear avoidance	NIH Task Force single item	Predictor/covariate	Patient self-report at baseline
Frailty	Frailty Index 	Predictor/covariate	Patient self-report at baseline and EHR data
Medical morbidity	Carey Ambulatory-based Morbidity Score 	Predictor/covariate	EHR data; based on last 12 months
Multiple non-malignant musculoskeletal pain conditions	1 pain cluster vs. >1 > 1 pain-related ICD-10 diagnosis corresponding to more than one (>1) of the non-malignant musculoskeletal chronic pain condition clusters developed for the National Pain Strategy chronic pain condition clusters  Back pain Neck pain Limb/extremity pain, joint pain and arthritic disorders Fibromyalgia Headache Orofacial, ear, and temporomandibular disorder pain Musculoskeletal chest pain General pain subcategory of the Other painful conditions cluster	Predictor/covariate	EHR data; diagnoses in participant's EHR extracted at baseline for prior 360 days
Mental health mood disorders	ICD-10 diagnosis for depression and/or anxiety diagnosis	Predictor/Covariate	EHR data; diagnoses in subject's EHR extracted at baseline for prior 360 days

Moderators & Predictors	Definition	Role	Data Source
COVID19 pandemic impact	Two questions modified from assessments designed by Pain Collaboratory. These focus on impacts of ability to get health care and on overall health	Time-varying covariate	Patient self-report
Sample Recruitment Time	Indicators of changes in sampling scheme to over-recruit certain racial and ethnic groups to improve representation and power for subgroup analyses	Covariate	Derived from randomization and changes in sampling distribution

#### 4. Sample Size and Treatment Assignment Procedures

We determined our sample size requirements for our primary outcome the RMDQ at 6-months that focuses on detecting differences of each acupuncture group compared to UMC. Recruited older adults with cLBP will be randomized, in equal proportions, to one of the three groups (UMC, SA, and EA). The power calculation below was conducted under assumptions of a 20% loss-to-follow-up rate and a SD of 6 points in RMDQ score in each arm (consistent or larger than results from previous trials), and that pairwise comparisons will only be conducted if the omnibus F-test is statistically significant at a 0.05 level to control for multiple comparisons (Fisher's Least Significance Difference multi-comparison approach). Given a sample of 789 total participants (263 per arm) among whom 630 (210 per arm) complete their 6-month follow-up data collection, we will have at least 90% power to detect a MCID of 2 points on the RMDQ score between each acupuncture group and UMC (pair-wise comparison power). Nevertheless, in the scenario where SA at 6-months attenuates to be equivalent to UMC and EA has a 2-point MCID improvement relative to both SA and UMC, we will have 91% power to detect a difference between SA and EA as well as between UMC and EA (each pair-wise comparison).

The above power calculation was conducted with RMDQ score as the outcome. When the outcome of interest is the change on RMDQ score from baseline to 6-month, we expect a smaller SD than 6 points in each arm (based on previous trial data conducted at KPWHRI only the SD RMDQ at 6 months was 5.42 and change in RMDQ was 5.11). Thus, we are sufficiently powered ( $\geq 90\%$ ) to detect MCID differences between all pairwise group comparisons. Power was calculated via simulation using R software version 3.6 accounting for multiple comparisons of the three study arms using Fisher's Least significant different approach. Note to be conservative we assumed a larger SD than we expect since we may have loss to power due to clustering of participants within acupuncture provider (acupuncturists may see 10-15 participants) and we may have more variability in baseline outcome since this trial is pragmatic across four health care systems. Inflating the SD by more than 15% ( $6/5.11=1.17$ ) should take into account both potential loss to power issues. Furthermore, although acupuncturists may see up to 10-15 participants at our smallest site (IFH) this accounts for 16% of our expected recruited sample (123 of 789 with only two-thirds of those randomized to an acupuncture arm where clustering is of issue). At other sites, the combination of HCS embedded and community acupuncturists are expected to result in much smaller caseloads (3-8 participants on average). In keeping with a pragmatic trial approach and to lower barriers to participant receipt of acupuncturists, we are motivated to include a larger number of acupuncturists serving participants in the study

For any two group comparisons, given our sample size of 210 per group and a SD of 6, the 95% CI width around the difference in means between groups is +/- 1.15 pts. Further, for secondary analysis for the binary outcome 30% improvement in RMDQ from baseline we have >90% power to detect an MCID assuming the probability of improvement in UMC was between 33%  and 44%  and the MCID was a 15% improvement above UMC for each of the acupuncture groups. We will use an intent-to-treat approach in which participants will remain as randomized regardless if they withdrawal from treatment or cross-over to other treatment arm (e.g. UMC participant seeks acupuncture outside of study).

## 5. Definition of Study Samples

### 5.1 Participants Inclusion and Exclusion Criteria

We will require all participants to meet all the following inclusion criteria in order to participate in the trial.

Inclusion Criteria	Rationale and Source
Is at least 65 years of age	Age range of the Medicare older adult population (EHR)
Is a current member or patient of the healthcare system	A method for identifying participants who have current and consistent contact with the healthcare system (EHR and PRO)
Visited a health care provider for low back pain within the past 12 months	A method for identifying potential participants who may have cLBP (EHR)
Received primary care at one of the participating health care systems.	Location of our study sites (EHR)
Has back pain that is uncomplicated with or without radicular pain.	This is the type of back pain we are studying. (EHR)
Back pain $\geq$ 3 months	Meets our definition of chronic back pain (PRO)
General activity question from PEG $\geq$ 3	Meets minimum definition of back dysfunction (PRO)
Primary care provider provides permission to contact patient	Ensures that there is no medical or related reason not to include patient (via email)
Willing and able (Callahan screener $\geq$ 3) to provide consent	Ethical requirement (PRO)

Persons who meet any of the exclusion criteria at baseline will be excluded from study participation.

Exclusion Criteria	Rationale
Specific types of back pain (metastatic cancer or bone cancer or secondary cancers, vertebral fractures, spinal infection, active inflammatory disease)	Other treatments are more appropriate than acupuncture for these specific causes (or likely causes) of LBP (EHR)
Low back surgery within past 3 months	May still be healing from surgery (PRO)

Receiving workers compensation or involved in litigation related to cLBP	Additional treatments may be required as there are disincentives to improve (PRO)
Acupuncture within the last 6 months	Ensures that they have not received acupuncture for this episode of care (PRO)
Does not speak or write English or Spanish	Cannot complete outcomes questionnaires or treatments (PRO)
Major psychosis, dementia	Unable to give adequately informed consent (EHR)
Current cancer treatment	Need for primary focus on cancer treatment (EHR)
Red flags of serious underlying illness (a fever most days in the last month, recent unexplained weight loss of 10 lbs or more)	Need to look for serious underlying illness to not delay any needed treatment for those. (PRO)
Living in a nursing home, on Hospice, or palliative care	Requires a different study design and logistics (EHR; confirm via PRO)
Non-speaking deafness	Cannot communicate with acupuncturists and study staff (EHR)
Non-reliable transportation	Cannot attend acupuncture treatments (PRO)

## 5.2 Intent-to-Treat (ITT) Sample

All study participants randomized meeting eligibility criteria prior to randomization will be included in the ITT sample and will be analyzed according to their assignment group at the time of randomization. Note we will exclude participants if they were randomized but after further review based on data collected prior to randomization the participants did not meet all eligibility criteria. These participants will be listed as protocol violations.

## 5.3 Safety Analysis Sample

The safety analysis will include all randomized participants in the sample in the 12-months period of follow-up.

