Recruitment procedures: [name], the site PI at IFH and a PCP, will inform his colleagues of the study and basic requirements for enrollment. PCPs will use basic eligibility criteria to guide patient referral to the study; an Epic smart phrase will be developed for PCPs that gives a brief synopsis of the study and phone number for the clinical research coordinator (CRC). PCPs will share the CRC's phone number with interested patients. In addition, PCPs will obtain permission from interested patient's to be contacted by the CRC. The CRC will check the patient's EHR to ensure that the patient meets basic inclusion/exclusion criteria and then send provisionally eligible patients an invitational letter with information about the study. The CRC will then call these patients referred for the study. Using a structured script, the CRC will ascertain continued interest in the study. If the prospective participant is interested in participating in the study, they will be asked to provide oral consent for screening and be administered the oral eligibility screener, which captures data that are not in the electronic health record (EHR). If the prospective participant meets the oral screening criteria and agrees to learn more about the study, they will be scheduled for a phone visit to have their questions answered and provide oral consent for the baseline and follow-up data collection, including HIPAA authorization. For study participants randomized to acupuncture and receiving at least one treatment, written consent for acupuncture treatments would be obtained at the first acupuncture visit and before treatment. IFH will also allow for the possibility of using method 2 (below), if recruitment via provider referral is not robust enough, *i.e.*, if recruitment and enrollment targets are not being met.

Method 2: Invitational letters (or emails) sent after identification of candidate participants using ICD-10 diagnoses from automated data: At KPNC, KPWA and SH, we will then send letters of invitation (KPNC, KPWA, SH) or emails of invitation via "MyChart" (SH), a HIPAA compliant secure web-based platform. At these participating HCSs, we expect this will be our primary method of recruitment.

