### **19.1 Adverse Event**

A non-serious AE will be defined as an unfavorable and unintended diagnosis, symptom, syndrome, or disease that occurs or worsens during the acupuncture intervention period and is plausibly related to acupuncture, including bleeding and needling pain. AEs will be collected in multiple ways: (1) during 3-, 6- and 12-month follow up assessments by querying whether the participant believed that anything about their acupuncture treatments caused significant discomfort or pain and, if so, how long that lasted; (2) via electronic acupuncturist treatment reports; and (3) from participants who may phone the study team at any time to report AEs. Because acupuncture has relatively short-term physiological effects, we will not report AEs that first manifest more than 30-days after a participant's final acupuncture treatment.

We will classify each non-Serious AE using the following definitions: Mild (transient or minimal symptoms; no changes in activity level; no therapy or only symptomatic therapy); Moderate (symptomatic with moderate changes in activity level; no decrease in social activities; specific therapy required); Severe (incapacitating; bed rest; substantial decrease in social activities; loss of work). These definitions are consistent with the International Council for Harmonisation (ICH) standards in characterizing AEs. In the unlikely event that an adverse effect occurs that requires medical care, treatment will be provided as covered by participants' existing health care coverage. We will also assess the likely relatedness of the adverse event and acupuncture given the nature of the event, the timing related to treatment and any important contextual factors.

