### **19.2 Serious Adverse Event**

For the proposed study, we are operationally defining a serious adverse event (SAE) as a death or hospitalization, prolongation of a hospitalization or other serious or life-threatening event during a patient's active participation in the trial and study acupuncture treatments. We will review/query active study participants' EHR data every month to identify deaths and hospitalizations among enrolled participants. In the case of a death, a chart review will be conducted by an independent physician at the clinical site to assess whether the death was related to the study intervention (definitely, probably, possibly, or unrelated to the study intervention). For hospitalization, a study clinician at each HCS will review the list of diagnoses for possible relatedness to the acupuncture intervention. For any diagnosis at least possibly related to acupuncture, a more in-depth examination of the medical chart will be conducted.

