## 19.4 Safety Outcomes

See DSMP for specifics.

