## 19.5 Descriptive Analysis

The safety outcomes will be summarized by type and by intervention in terms of frequency of the event in each individual, number of participants having the event, timing relative to randomization, and relatedness to the study treatment (definitely, probably, possibly, definitely not). As acupuncture is a relatively safe treatment, we anticipate incidence of possibly treatment related hospitalizations and deaths to be relatively rare so do not propose any formal statistical tests of the SAE data.

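### Non-serious acupuncture adverse events need a treated-only denominator and a per-session rate alongside the all-randomised safety summary

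*SAP*

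**What the plan says.** SAP 5.3 defines one sample for all safety summaries: "The safety analysis will include all randomized participants in the sample in the 12-months period of follow-up".

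SAP 19.1 defines a non-serious adverse event (AE) as one that "occurs or worsens during the acupuncture intervention period and is plausibly related to acupuncture, including bleeding and needling pain". Events that first appear more than 30 days after the last treatment are not reported. Serious events are defined more broadly. SAP 19.2 is "operationally defining a serious adverse event (SAE) as a death or hospitalization, prolongation of a hospitalization or other serious or life-threatening event", and deaths and hospitalisations are sought by a monthly health-record query of active participants.

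Under SAP 19.5, safety outcomes are "summarized by type and by intervention in terms of frequency of the event in each individual, number of participants having the event", with timing counted from randomisation and a relatedness grade. SAP 19.4, on safety outcomes, says only "See DSMP for specifics". That monitoring plan is not among the documents.

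The protocol foresees people who are assigned acupuncture and never have it. Protocol 4.3.1.2 says: "For study participants randomized to acupuncture and receiving at least one treatment, written consent for acupuncture treatments would be obtained". Protocol 9.3 describes participants randomised to acupuncture who received none. Protocol 5.1 says that not all visits need be completed to stay in the study. The same section has the acupuncturist submit, for each session, the date, visit number, disposition and any reported AEs.

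On ascertainment, Protocol 7.2 and 7.3 send the AE questionnaire to all acupuncture-randomised participants at 3 months and to EA alone at 6 months. SAP 19.1 has the question asked at the 3-, 6- and 12-month assessments and names no arm.

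**The concern.** The protocol presents safety in older adults as an evidence gap and expects the results to inform Medicare, physicians and patients. Their question about needling harms is what happens to a person who has acupuncture, and how much risk each further session adds. The summary in SAP 5.3 and 19.5 answers neither directly.

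People who never attend a session cannot have an event from study needling, yet they are in the denominator. EA participants are offered more sessions than SA participants, so a larger EA count is expected even if each session carries the same risk. A reader of arm totals could not tell whether maintenance needling is riskier or only more frequent. If EA participants are also asked about AEs once more than SA participants, part of an arm difference could come from the asking.

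**Working it through.** **The plan's own figure.** The documents state no safety rate and no safety sample size. The arm size that an all-randomised summary would use does reproduce: 210 / (1 − 0.20) = 262.5, rounded up to 263; 3 × 263 = 789.

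**Inputs**
- Randomised per arm: 263 (Protocol 9.2, SAP 4).
- Sessions in SA: proposed minimum 8, maximum 15 (SAP 1.3).
- Sessions in EA: a further 4 to 6, so 8 + 4 = 12 to 15 + 6 = 21 (SAP 1.3).
- Background rate: bleeding and haematoma in 1 to 10 per 100 patients (Protocol 7.2). The upper end is used for illustration.
- Non-starter share f: not given; 5%, 10% and 20% are assumptions.
- Per-session risk s: not given; 0.1% to 2% is an assumption, taken as independent between sessions and equal in both arms.

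**Step 1, dilution.** Proportion on all randomised = p × (1 − f), where p is the proportion among treated participants.
- f = 5%: 10% × 0.95 = 9.5% (about 250 of 263 treated)
- f = 10%: 10% × 0.90 = 9.0% (about 237 treated)
- f = 20%: 10% × 0.80 = 8.0% (about 210 treated)

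The relative understatement equals f whatever p is.

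**Step 2, number of sessions.** With equal risk per session, expected event counts are in the ratio 12/8 = 1.50 at the proposed minimum and 21/15 = 1.40 at the maximum. The proportion with any event after k sessions is 1 − (1 − s)^k:

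| Assumed risk per session | Sessions SA / EA | SA, any AE | EA, any AE | Ratio |
|---|---|---|---|---|
| 0.1% | 8 / 12 | 0.80% | 1.19% | 1.50 |
| 0.1% | 15 / 21 | 1.49% | 2.08% | 1.40 |
| 1% | 8 / 12 | 7.7% | 11.4% | 1.47 |
| 1% | 15 / 21 | 14.0% | 19.0% | 1.36 |
| 2% | 8 / 12 | 14.9% | 21.5% | 1.44 |
| 2% | 15 / 21 | 26.1% | 34.6% | 1.32 |

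**Step 3, the same data per session.** At the maximum, SA has 263 × 15 = 3,945 sessions and EA 263 × 21 = 5,523. At 1% per session the expected events are 39.45 and 55.23. Both give 10 per 1,000 sessions, a ratio of 1.0.

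**Step 4, ascertainment.** Under Protocol 7.2 and 7.3, SA gets one AE questionnaire (3 months) and EA two (3 and 6 months). Under SAP 19.1, no arm is excluded from three rounds (3, 6 and 12 months). These are different data-collection schemes, and a per-session rate would not by itself correct for the difference.

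**The case against.** The strongest reply is that the SAP describes its safety section as a brief outline, defers safety outcomes to the monitoring plan, and directs these analyses to the Independent Monitoring Committee. They are descriptive, and SAP 19.5 lists counts, not percentages. A treated-only or per-session table may already exist in the monitoring plan. This stands as a limit: the absence can be asserted only for the protocol and SAP. It does not remove the point, because the sample and the summary are set in the SAP itself.

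The dilution may also be small. At 263 per arm, a 10% proportion has a standard error of √(0.10 × 0.90 / 263) = 1.85 percentage points. A loss of 0.5 to 1.0 point at 5% to 10% non-starters is well inside that. This is fair, although dilution always acts downward and does not shrink with sample size.

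Timing from randomisation can be defended as one descriptor among several, since participants are asked to attend first within 10 days. Timing from the latest session is still the more informative clock for effects that SAP 19.1 calls short-term.

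Three stronger readings are tempting, and the documents do not support them:
- That the EA comparison is confounded by its extra sessions. Those sessions are the EA treatment, and arms are randomised. A higher cumulative count in EA is a valid effect of assignment and useful to a payer; it is only silent on risk per session.
- That usual care must have no events by definition. SAP 19.1 requires a plausible relation to acupuncture, not to study acupuncture, and the plan foresees usual-care participants seeking acupuncture elsewhere. A low count there would come largely from the protocol questionnaire, which goes only to acupuncture-randomised participants and asks about study treatment.
- That a single rate would be taken over all 789. SAP 19.5 reports by intervention.

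**Conclusion.** The point holds as a specific gap. All randomised participants are the right sample for serious events. For non-serious events tied to acupuncture, the protocol and SAP give no summary among people who were treated and no rate per session, though the data for both are collected.

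The size cannot be fixed from the documents. The understatement equals the non-starter share: 10% becomes 9.5% to 8.0% under an assumed 5% to 20%, if a proportion on the SAP 5.3 sample is reported. With equal per-session risk, EA would show about 1.3 to 1.5 times the SA proportion with any event. That range assumes per-session risks of 0.1% to 2%, independence between sessions, and attendance by everyone at either the proposed minimum or the maximum.

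The difference between the protocol and the SAP on AE questioning is a separate inconsistency, clear from the text, that bears on the same SA–EA contrast.

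**What to change.** Keep all randomised participants for serious events, deaths and hospitalisations. For non-serious acupuncture AEs, add to SAP 5.3 and 19.5:

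- a summary for SA and EA among participants with at least one study session;
- a rate per 100 or 1,000 study sessions;
- SA and EA pooled for the standard period, with EA maintenance shown separately (SAP 13 already combines the two arms at 3 months as the same intervention);
- timing from the most recent session.

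If the monitoring plan already provides this, cite the section in SAP 19.4 instead. State also whether by intervention in SAP 19.5 means assigned or received.

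Reconcile Protocol 7.2 and 7.3 with SAP 19.1 on which arms are asked about AEs and at which time points, and report what was actually done in each arm.

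The cost is SAP wording and one further table from treatment records already collected. The downside is that two safety denominators must be explained.
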